Common Treatments for Common Colds: A Pilot Study

RESEARCH PROTOCOL

[**Squirting Nasal saline solution Or Routine Treatment (SNORT) Study**]

Investigators

[name], [name], [name], [name], [name]

Aims

This project aims to compare the effectiveness of the addition of nasal saline spray to routine care for minimisation of the symptoms of acute URTIs. It also aims to assess the feasibility of conducting a randomised controlled trial for this purpose in general practice and to refine the processes of the trial.

Synopsis

Over the last few years, the National Prescribing Service (NPS) (<http://www.nps.org.au/>) has conducted regular campaigns aimed at educating the public about appropriate treatments for the common cold. They have continually reinforced the message that common colds are caused by viruses, and therefore antibiotics are likely to have no benefit. The NPS have produced resources to educate the public that treatments such as nasal saline, steam inhalation and decongestants that relieve symptoms are more helpful than antibiotics for common colds and viral upper respiratory tract infections.

However, the effectiveness of isotonic nasal saline spray for relief of common cold or acute rhinosinusitis symptoms has not been adequately evaluated – most studies have been too small or of poor methodological quality. Therefore this pilot study aims to determine the feasibility of conducting a general practice based, randomised controlled trial to assess the efficacy of nasal saline spray on the duration of general unwellness and symptoms associated with the common cold or acute rhinosinusitis.

In this study, consenting patients who have visited their GP because of a common cold or acute rhinosinusitis will be randomised to either nasal saline spray plus usual care or usual care alone. All study participants will be requested to not use steam inhalations, or any nasal decongestants or nasal sprays other than the trial medication for the duration of their participation in this study. The duration of general unwellness, cough, runny or blocked nose and sore throat, as well as the use of other treatments including antibiotics will be compared in both groups. Patients will be followed up until their first day of wellbeing or for 6 weeks, whichever occurs first.

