Participant recruitment – Participating GPs will opportunistically identify potentially eligible patients as they present for a consultation for treatment of the common cold or acute rhinosinusitis, and initiate discussion to gauge interest and determine eligibility. Following this consultation, the Practice Nurse (or another suitable staff member) will continue discussions with potentially interested patients, answer their questions, and obtain informed consent.

Inclusion criteria

- Patient is aged 2+ years and has had symptoms of cold (runny nose, sore throat, sneezing, cough lethargy etc), or acute rhinosinusitis for at least 5 days and up to but not more than 3 weeks.

Exclusion criteria

Patients who:

- wish to use any treatment involving a volume of liquid going into the nose (e.g. steam inhalations, nasal sprays, nasal decongestant agents nasal douches, neti pot etc). Participants who have previously been using these may be included, provided they agree to discontinue use for the duration of their participation in the study

OR who have:

- known or suspected Chronic Obstructive Pulmonary Disease (COPD)
- suspected pertussis infection
- facial anatomical abnormalities
- cognitive impairment preventing informed consent
- physical impairment preventing compliance with the study protocol

Recruitment of participating GPs – there is a core group of GPs & associated general practices who have been involved in the development of this project – UQ Health Services ([name], [name], [name]), Inala Indigenous Health ([name]) and Inala Primary Care. It is expected that additional GPs will be recruited through the South East Queensland Research Network (a network of GPs who have participated in general practice based, clinical research) and the UQ General Practices of Research Excellence (GPs who have lead clinical research in their own practices).

Sample Size – 60 participants, 30 in each group.

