Randomisation and allocation to study groups – patients will be randomised to either the intervention or control group. Randomising will be done at the Discipline of General Practice using computer generated random sequences in blocks of ten patients. A set of sealed, opaque, sequentially numbered study packs will be delivered to each participating general practice. Once a patient has consented to participate in the study, they will be allocated a study identifier, and will be given a study pack. The study pack will contain the first fortnight's patient diary, and sufficient study medication for a fortnight. Study packs for the control group will contain 3 packs of Vicks Vapor Drops or similar, of comparable size to the nasal saline spray. This will be a 'thank you' to control group participants and will ensure that all study packs look similar such that practice staff and patients remain blinded to group allocation.

Intervention – the intervention is a nasal saline solution which will be used for a minimum of 4 times per day.

Control – patients allocated to the control group will use usual care treatments only.

Primary outcome measure is the return of wellness, indicated by the patients' assessment of the first day of wellbeing.

Secondary outcome measures include:

1. severity and duration of troublesome nasal stuffiness
2. severity and duration of troublesome cough
3. severity and duration of rhinorrhea
4. severity and duration of malaise
5. antibiotic use
6. adverse effects of treatment
7. patient compliance
8. patient satisfaction.

Data collection – The data will be collected through patient diaries. Patients will be completed on a daily basis until general wellbeing is restored or for 6 weeks, whichever occurs first. Answers will be an indicator of the patients' subjective assessment of the severity of the symptoms each day. Restoration of general wellbeing is defined as when the patient answers 'yes' to the question 'Are you well

again?'. The diary has been adapted from one used by general practice researchers in the UK.⁷

A patient enrolment form will be used to gather basic demographic information, the duration of unwellness prior to attending the GP, and the patient's belief about the effectiveness of antibiotics for treating common cold or acute rhinosinusitis.

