Patients' satisfaction with their involvement in the study and, for the nasal saline group, use of the study medication, will be assessed at the time of the final follow-up phone call by asking for patient feedback.

Follow-up – All study patients will be contacted by telephone by the Research Assistant (RA) within 2-3 days of recruitment to ensure understanding and willingness to comply with the study protocol. The RA will contact the patients again 7-9 days after recruitment to determine if symptoms have resolved or whether the patient requires another study pack. A third follow-up call will occur at about day 20, and a third study pack sent out as required. Any patients continuing the treatment / diary at the third call will receive a final follow up telephone call at 6 weeks post enrolment into the study to remind them to send back the symptom diary. The RA will remain blinded to the group to which the patient has been allocated throughout the follow-up period. Another member of staff will make up additional study packs as required.

Analysis – Data will be analysed according to the intention-to-treat principle, comparing the intervention group with the control group. Baseline characteristics and symptoms will be compared using either Student's t-test (for continuous data) or Fisher's Exact Test (for categorical data). We will analyse first day of well-being using Cox regression survival analysis, and will adjust for baseline symptom severity, and duration of illness before visiting the GP. We shall investigate the severity of illness using a symptom score collected on day 3 after enrolment. We will use a multivariate linear regression, adjusting for baseline symptom severity, and duration of illness before visiting the GP. A P-value < 0.05 will be considered statistically significant. There will be no adjustment for multiple comparisons.

Dissemination of results – The outcomes of this study will be disseminated through presentations at relevant conferences, and publication in international peer reviewed journals.

Potential Benefit of Findings

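### The diary stops on the first well day, so patients who are well on day 1 or 2 have no day-3 score for the severity analysis

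*Protocol*

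**What the plan says.** All references are to the Protocol.

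- **Methods, Data collection.** "The data will be collected through patient diaries". The diary is "completed on a daily basis until general wellbeing is restored or for 6 weeks, whichever occurs first". The end point of that rule is then fixed: "Restoration of general wellbeing is defined as when the patient answers" yes to the well-again question.
- **Synopsis.** The same limit applies to follow-up: "Patients will be followed up until their first day of wellbeing or for 6 weeks, whichever occurs first".
- **Methods, Analysis.** Data are to be analysed by intention to treat. For severity, "We shall investigate the severity of illness using a symptom score collected on day 3 after enrolment". The model follows: "We will use a multivariate linear regression, adjusting for baseline symptom severity, and duration of illness before visiting the GP".
- **Methods, Follow-up.** The only contact near day 3 is a telephone call 2-3 days after recruitment. Its stated purpose is to check understanding and willingness to comply. Symptom scoring is not mentioned.
- **Inclusion criteria.** Patients enter after having symptoms "for at least 5 days and up to but not more than 3 weeks".

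**The concern.** The diary rule and the severity analysis do not fit together. The event that ends the diary is the primary outcome, the first day of wellbeing. A patient who reaches it on day 1 or 2 is told to stop recording before the score used for severity is due. Because entry requires at least 5 days of illness and allows up to 3 weeks, recovery that soon after enrolment is possible.

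The scores that go missing belong to the patients who did best. If saline works, more of them will be in the saline arm. A comparison limited to patients with a score then conditions on something that happened after randomisation. Adjusting for baseline severity and prior duration of illness does not generally undo that. Severity stands beside duration in the first research question, and this is the only severity analysis described. The pilot is also meant to refine the trial's processes, so the mismatch could carry over into a larger study.

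**Working it through.** The protocol gives no figure to reproduce: 60 patients are stated without effect size, SD or recovery rate. The mismatch follows from the text. Its size rests on assumptions.

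**1. Who has a score under the stated rules**

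| First well day | Last diary day | Day-3 score |
|---|---|---|
| 1 | 1 | none |
| 2 | 2 | none |
| 3 | 3 | recorded |
| 4 or later | 4 or later | recorded |

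Only recovery before day 3 matters.

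**2. How many might be well by day 2 (assumption)**

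For a Weibull time to wellness with median m days and shape k, the share well by day 2 is 1 − 2^(−(2/m)^k). For example, m = 10 and k = 2 gives 1 − 2^(−0.04) = 2.7%.

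| Median m | k = 1.0 | k = 1.3 | k = 2.0 |
|---|---|---|---|
| 5 | 24% | 19% | 10.5% |
| 7 | 18% | 13% | 5.5% |
| 10 | 13% | 8% | 2.7% |
| 14 | 9% | 5% | 1.4% |

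The assumed range is therefore about 1% to 24%. Nothing in the protocol narrows it.

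**3. Effect on the severity difference if only patients with a score are analysed**

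Assumptions: latent day-3 severity is normal with SD 1; saline lowers it by d = 0.3 or 0.5; a share p of controls is well before day 3, at the low-severity end; early recovery correlates with severity at ρ = 0.7 or 1.0. Let c = Φ⁻¹(p) and λ(z) = φ(z)/(1 − Φ(z)). Then:

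- share of saline patients without a score = Φ(c + d)
- difference among patients with a score = −d + ρ[λ(c + d) − λ(c)]

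Example with p = 10%, d = 0.5, ρ = 1: c = −1.282, λ(c) = 0.195 and λ(c + d) = 0.376, so the difference is −0.5 + 0.181 = −0.319. With ρ = 0.7 it is −0.5 + 0.126 = −0.374.

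| p (controls) | Controls without score, of 30 | Saline without score, of 30 | Loss of effect, SD | Loss, % of d |
|---|---|---|---|---|
| 0% | 0 | 0 | 0 | 0 |
| 1.4% | 0.4 | 0.9-1.3 | 0.02-0.06 | 7-13 |
| 3% | 0.9 | 1.7-2.5 | 0.04-0.10 | 12-19 |
| 5% | 1.5 | 2.7-3.8 | 0.05-0.13 | 16-26 |
| 10% | 3.0 | 4.9-6.5 | 0.07-0.18 | 23-36 |
| 20% | 6.0 | 8.8-11.0 | 0.10-0.24 | 32-49 |
| 24% | 7.2 | 10.3-12.5 | 0.10-0.26 | 35-53 |

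Ranges run over both values of d and of ρ. With d = 0 the formula gives a difference of zero, so in this model the selection creates no effect where there is none. If every patient has a recorded day-3 score, the expected difference is −d.

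**4. Scale**

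With 30 per arm the unadjusted standard error is √(2/30) = 0.26 SD. For 80% power at two-sided 0.05 the difference must be (1.960 + 0.842) × 0.258 = 0.72 SD. Loss of numbers alone costs little: power for 0.72 SD falls from 80% at 30 per arm to 76% at 27 and 71% at 24.

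**The case against.** **The analysis plan can deal with it.** How a recovered patient enters the model is a derivation or missing-data rule, and an analysis plan may exist. This stands in part. Such a plan could assign a value, but it would be imputing scores that the protocol tells patients not to record. The collection rule belongs to the protocol.

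**A reader might infer that the protocol prescribes a complete-case analysis and so contradicts intention to treat.** It does not. The Analysis paragraph names the principle, the outcome and the covariates, and nowhere limits the model to patients with a score. The conflict arises only if the analysis is done that way. It would also be wrong to say that only patients still unwell on day 3 have a score, since a patient first well on day 3 should have an entry for that day.

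**A reader might infer that the bias is known to be large.** The protocol does not support that. The recovery rate is assumed throughout, and the design anticipates persistent illness: at least 5 days ill at entry, fortnight packs, a first call about resolution at 7-9 days and a third pack at about day 20. That does not show early recovery to be rare, but the low end of the range is as defensible as the high end.

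**Little depends on it.** Largely true. This is a secondary outcome in a pilot of 60. The Cox analysis counts every early recovery as an event. At 10% early recovery the loss of 0.07-0.18 SD is below the standard error of 0.26 SD. This limits how serious the point is, but does not remove it.

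**Well means a score of zero.** The protocol does not say so. The well-again question is a global one, and a patient may answer yes with some cough remaining. Assigning zero is an assumption, so collecting the score is better.

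**Conclusion.** The point holds as a mismatch between data collection and analysis. By the protocol's own rules the day-3 score is missing for patients who reach the primary outcome on day 1 or 2. An analysis limited to patients with a score would not compare all randomised patients and, if saline works, would usually understate its effect on severity.

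The size cannot be fixed from the protocol. Under the assumptions above it runs from no bias to about half of a 0.3-0.5 SD effect, depending mainly on how many recover before day 3. Neither the primary analysis nor the feasibility aims are affected. This is a low-cost improvement that should be made, and it does not invalidate the trial.

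**What to change.** - **Data collection.** Instruct every randomised patient to complete the symptom items through at least day 3, whatever the answer to the well-again question. The first day of wellbeing stays defined as it is.
- **Follow-up.** Use the existing 2-3 day call to remind patients of this.
- **Analysis.** State that all randomised patients enter the day-3 severity model. Where a patient already declared well still has no day-3 entry, use the scale's no-symptoms value, stated in advance. Add a sensitivity analysis with other values, because feeling well may coexist with residual symptoms.

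The cost is one diary instruction, a short addition to the call and to the analysis paragraph, and at most two extra diary days (days 2 and 3) for a patient well on day 1. It works only for patients who have not yet passed day 3. For any others, only the fallback value and its sensitivity analysis remain.
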